4.3 Primary Endpoint Analysis

4.3.1 Definition of Endpoint(s)

The primary efficacy endpoint is change from baseline in hours of ventilation support at Week 24.

The hours of ventilation support will be based on diary data from participants for whom diary data was collected at baseline (those administered AT132 under protocol v5 and beyond, including all participants in Part 2), and by assessment of time off ventilator questionnaire for all other participants (those administered AT132 under protocol v4 and prior). Weekly scores will be the average of ventilation hours needed for at least 5 out of the 7 days leading up to and including the analysis visit day (e.g., Day 168 for Week 24). For cases where the diary or the ventilator assessment indicates that ventilator type = "None", then zero will be imputed for the number of hours on ventilator.

The days included for the average for the particular visit week are defined by $\text{avisit} = \text{"Week"} \parallel \text{strip}(\text{put}(\text{ceil}(\text{ady}/7), \text{best.}))$, where ADY = the analysis visit day of the diary entry.

If at least 5/7 days of the visit week are non-missing, then the remaining missing values will be ignored in the calculation of average ventilation hours needed. Otherwise, if <5 non-missing diary records are available for the visit week, then up to 4 missing values will be imputed by the worst score of the week (most hours on ventilator), so that at least 5 records are available for calculating the average for the week.

Baseline is defined as the average of the diary data values in the 7 days leading up to and including the day of administration of the study drug (i.e. Analysis Day – 6 through Day 1). The missing data approach described in the paragraph above will be used if <7 days of data are available at baseline. If only non-diary ventilator questionnaire data is available at baseline, the last record prior to administration of study drug will be used for the baseline value.

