Following the occurrence of fatal serious AEs (SAEs) in Study ATX-MTM-002, the Sponsor, in consultation with the DMC and external experts, evaluated the data and reassessed the benefit/risk profiles of the 1.0×10^{14} vg/kg and 3.0×10^{14} vg/kg dose levels. As of the data cutoff date of 08 July 2020, 5 subjects who received 3.0×10^{14} vg/kg AT132 developed AT132-related SAEs involving the hepatobiliary system. In 2 subjects, these SAEs resolved; in 3 subjects, fatal events occurred subsequent to severe cholestatic liver dysfunction. Within the 3.0×10^{14} vg/kg dose level cohort, 8 of 17 subjects (47.1%) experienced 26 SAEs considered related to AT132. In contrast, within the 6 subjects dosed at the 1.0×10^{14} vg/kg dose level, all of whom are ≥ 2 years from AT132 administration, 1 (16.7%) subject experienced 4 AT132-related SAEs, all resolved, and none involved the hepatobiliary system. In addition to a favorable safety profile observed in the subjects treated with 1.0×10^{14} vg/kg, a clinically meaningful benefit continues to be observed in this group at last follow-up. In this group, which had a mean 20.5 hours (SE 2.02) of ventilation per day at baseline ($n = 5$ [83.3%] with invasive ventilation; $n = 1$ [16.7%] with non-invasive ventilation), 5 out of 6 (83.3%) subjects were ventilatory independent at last follow-up (as of data cutoff date 08 July 2020). With respect to gross motor development, at baseline 5 of the 6 subjects did not perform any of the following major motor milestones: sit unassisted for 30 seconds, raise self to standing position, stand alone, or walk alone. At baseline, 1 subject did sit unassisted for 30 seconds but did not perform the remaining motor tasks. At last follow-up following AT132 administration at 1.0×10^{14} vg/kg, 5 out of 6 subjects performed all of these motor tasks, including walking alone. Regarding performance on the Children's Hospital of Philadelphia Infant Test of Neuromuscular Disorders (CHOP INTEND), this 1.0×10^{14} vg/kg group demonstrated a baseline mean score of 37.7 (SE 2.42). At last follow-up, performance had improved to a mean score of 56.5 (3.97).

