3.3 Selection of Study Population

3.3.1 Inclusion Criteria

Subjects must meet all of the following inclusion criteria to be eligible for participation in this study. Subjects assigned to delayed-treatment control will be evaluated to confirm the subject still meets a subset (*) of the inclusion/exclusion criteria before receiving AT132.

1. Subject has a diagnosis of XLMTM resulting from a genetically confirmed mutation in the *MTM1* gene as assessed by a Sponsor-approved testing facility.*
2. Subject is male.*
3. Subject is aged less than 5 years old at dosing.*
4. Subject requires mechanical ventilatory support:
 - Part 1: Subject requires some mechanical ventilatory support (eg, ranging from 24 hours per day fulltime mechanical ventilation, to noninvasive support such as continuous positive airway pressure [CPAP] or bilevel positive airway pressure [BiPAP] during sleeping hours).
 - Part 2: Subject requires invasive mechanical ventilatory support ranging from 20 to 24 hours per day at screening (confirmed by daytime polysomnographic study).
5. Subject requiring invasive mechanical ventilator support is fitted with or willing to be fitted with a cuffed tracheostomy tube for some respiratory assessments.*
6. Subject has ventilator maximum positive end-expiratory pressure (PEEP) < 8 cmH₂O at screening.*
7. Signed informed consent by the parent(s) or legally authorized representative (LAR) (when applicable).*
8. Subject and parent(s)/LAR(s) are willing and able to comply with study visits and study procedures.*
9. UNIQUE to France: Subject's weight is ≥ 4.8 kg.

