7.4.2 Efficacy Analysis

7.4.2.1 Analysis of Primary Efficacy Endpoint

The primary efficacy endpoint is change from baseline in hours of ventilation support at Week 24. The hours of ventilation support will be based on diary data from subjects for whom diary data was collected at baseline (those administered AT132 under protocol v5 and beyond, including all subjects in Part 2), and by assessment of time off ventilator questionnaire for all other subjects (those administered AT132 under protocol v4 and prior). Weekly scores will be the average of ventilation hours needed for at least 5 out of the 7 days. Missing values will be ignored if number of ventilation hours are available for at least 5 days, otherwise they will be imputed by the worst score of the week.

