4.3.3 Sensitivity Analysis

In order to assess the robustness of the primary analysis model with respect to non-monotone missing data, the primary efficacy endpoint will be analyzed using a mixed model repeated measures (MMRM) with baseline, treatment (low dose or high dose), time (all available visit weeks through Week 48), and treatment by time interaction as fixed effects and participant as

random effect. The change from baseline in hours of ventilation support at Week 24 will be summarized by dose level based on this model, including the 95% confidence interval.

The same analysis set and data used for the primary analysis (including imputations) will be used for the sensitivity analysis.

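### The worst-day fill for missing ventilator-diary days is also applied at baseline, where it can only enlarge an affected child's apparent improvement; the SAP also gives two different baseline windows

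*SAP*

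**What the plan says.** SAP 4.3.1 averages diary hours over a seven-day visit week. With five or more recorded days, missing days are ignored. With fewer than five, "up to 4 missing values will be imputed by the worst score of the week (most hours on ventilator"), so that five records are available. The section then turns to the reference value: "Baseline is defined as the average of the diary data values in the 7 days leading up to and including the day of administration" of study drug, which it spells out as Day -6 through Day 1. It adds: "The missing data approach described in the paragraph above will be used if <7 days of data are available at baseline". Children who have only the questionnaire are handled differently: "the last record prior to administration of study drug will be used for the baseline value", with no filling.

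Protocol 7.4.2.1 has the same fill for weekly scores ("otherwise they will be imputed by the worst score of the week") and does not mention baseline. SAP 4.3.3 describes the only sensitivity analysis of this endpoint and states: "The same analysis set and data used for the primary analysis (including imputations) will be used for the sensitivity analysis".

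SAP 4.10.2, Table 11, which governs weekly diary averages, gives the baseline window as Day -7 to Day -1 and puts Day 1 in Week 1 (Days 1 to 7).

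**The concern.** Fewer hours is better, and the endpoint is the Week 24 value minus the baseline value. Replacing a missing day by the child's highest recorded day therefore acts in opposite directions at the two ends: at Week 24 it reduces the apparent benefit, at baseline it increases it. The reported quantity is the mean change within each dose group, and control-period data are excluded, so no comparator cancels a baseline error. The sensitivity analysis reuses the imputed data and cannot show the effect.

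The exposure is also uneven. Only children with a diary baseline (dosed under protocol v5 or later) can be affected, and these are mainly in the high-dose group.

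The window conflict is a separate fault. Two programmers following different parts of the SAP would derive different baselines for the same child, one of them including the dosing day, which then also counts in Week 1.

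**Working it through.** **Plan figures.** The documents give no figure for the effect of the fill. The 13 h planning effect (SAP 4.9) serves only as a yardstick. Its sample size reproduces with a two-sided t-test (sidedness is not stated): SD 6 gives power 0.72 at 4 per arm and 0.85 at 5 per arm, hence N = 10.

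**Size of the fill.** Let k be the number of recorded baseline days, with k < 5, reading the rule as filling up to five records.

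- Filled baseline = (sum of recorded days + (5 - k) x max) / 5
- Rise over the recorded-day mean = (5 - k)/5 x (max - mean), which is never negative

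The rise is zero with one recorded day, with equal days, and with 5, 6 or 7 recorded days.

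**Largest rise if days lie within 20-24 h.** This is the Part 2 entry range (Protocol 3.3.1: "Subject requires invasive mechanical ventilatory support ranging from 20 to 24 hours per day at screening"). The maximum has one day at 24 and the rest at 20, so max - mean = 4(k - 1)/k.

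| k | (5 - k)/5 | max - mean | Rise (h) |
|---|---|---|---|
| 2 | 0.6 | 2.00 | 1.20 |
| 3 | 0.4 | 2.67 | 1.07 |
| 4 | 0.2 | 3.00 | 0.60 |

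Examples: days 20 and 24 give 22.0 unfilled and (44 + 72)/5 = 23.2 filled; days 20, 20 and 24 give 21.33 and (64 + 48)/5 = 22.4.

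**Average rise, assuming recorded days spread evenly over a range r.** The formula is (5 - k)/5 x (k - 1)/(2(k + 1)) x r, which is 0.10r, 0.10r and 0.06r for k = 2, 3, 4. With r = 4 h this is 0.40, 0.40 and 0.24 h; with r = 2 h it is 0.20, 0.20 and 0.12 h.

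**Who is exposed.** Protocol 1.4.2 says the six original low-dose children were all at least 2 "years from AT132 administration" at the 08 July 2020 cutoff, so they were dosed by 08 July 2018. Protocol v5 is dated 01 May 2019, so they use an unfilled questionnaire record. Three controls were still undosed at v8 (SAP 1.2) and two were never dosed (SAP 1.3). Assuming no replacement, 3 - 2 = 1 low-dose child can have a diary baseline, in a group of 6 + 1 = 7. The high-dose group has 17 children (Protocol 1.4.2).

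**Shift in an unadjusted group mean per affected child, within 20-24 h.**

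- High dose: 1.2/17 = 0.07 h at most
- Low dose: 1.2/7 = 0.17 h at most

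**Windows.** With no Day 0, both windows have seven days and share Days -6 to -1. With complete diaries the two baselines differ by (Day 1 - Day -7)/7, at most 4/7 = 0.57 h in either direction within 20-24 h. The choice can also switch the fill on. Suppose only Days -6, -5, -2, -1 and 1 are recorded, as 20, 20, 22, 24 and 20 h:

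- 4.3.1 window: five days, 106/5 = 21.2 h
- Table 11 window: four days, filled, (86 + 24)/5 = 22.0 h

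The SAP's mapping code, ceil(ady/7), does not settle the matter: it gives 0 for Days -6 to -1, -1 for Day -7 and 1 for Day 1, so it produces neither window.

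**The case against.** Most of the case on the other side concerns size, and much of it stands.

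- **Direction.** The rise is measured against the recorded days. If the missing days were worse than any recorded day, the filled value is still too low: three recorded days at 20 h and four missing days at 24 h have a true mean of (60 + 96)/7 = 22.3 h, against a filled value of 20 h.
- **Offset.** A fill at Week 24 works the other way, so the net direction depends on where days are missing. Baseline is also a covariate in the MMRM, which spreads part of a shift across both dose groups; the group figures above apply to the unadjusted summary.
- **Scope.** Not all 17 high-dose children have diary baselines, since Cohort 2 had Week 24 data before v5. Conversely, Part 1 admitted children with less support, and one dosed under v5 or later could vary more: within-week ranges of 8 h or 16 h would give maxima of 2.4 h or 4.8 h. The 20-24 h bounds are conditional.
- **Consequence.** There is no hypothesis test, and the number of affected children could be zero.
- **Symmetry.** One rule at both time points can be defended as consistent, and the protocol's weekly rule does not exclude baseline. But the same arithmetic has the opposite effect on the endpoint at the two ends, so equal wording is not equal caution.
- **Day 1.** A dosing-day entry may describe mainly pre-dose time. The documents do not say so, and the general baseline definition (SAP 4.10.1), Table 9 and the questionnaire rule all use pre-dose data.

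These points limit the size of the problem. They do not change what the two SAP passages say.

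**Conclusion.** Both parts hold. Relative to the recorded days, the baseline fill can only leave a child's apparent improvement unchanged or enlarge it, and the planned sensitivity analysis cannot detect this. It affects only children with a diary baseline and 2 to 4 unequal recorded baseline days. The expected size is small: at most 1.2 h for such a child if days lie within 20-24 h, and under the even-spread assumption 0.12 to 0.40 h on average. The group-level bias cannot be computed because the documents give no missing-diary counts.

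The two baseline windows cannot both be programmed. Although the numerical effect is modest, the primary endpoint needs a single reference value. The change should be made because the text is wrong as written and cheap to correct; nothing here suggests that the overall result would change materially.

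**What to change.** In SAP 4.3.1, restrict the worst-day fill to post-baseline weeks and define the diary baseline as the mean of the recorded days, without filling. Use one pre-dose window, Day -7 to Day -1 as in Table 11, in both 4.3.1 and Table 11, and limit the ceil(ady/7) mapping to post-dose days. Listing the number of recorded baseline days per child would show which baselines rest on few records.

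The cost is two sentences of SAP text before database lock, plus the mapping note, with no new data. If the first lock has passed, the change can be documented in the clinical study report, as SAP section 1 provides. The fill change makes the reported improvement slightly smaller for children with 2 to 4 unequal recorded baseline days; the window change can move a baseline either way.

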4.3.2 Main Analytical Approach

The change from baseline in hours of ventilation support at Week 24 will be analyzed using a MMRM with treatment (low dose or high dose), time (Weeks 1, 4, 12, 16, 24, 36, and 48), and treatment by time interaction as fixed effects, baseline value of hours of ventilation support as the covariate, and within-participant repeated measure structure in the model.

To account for repeated measures within participants, the following within-participant covariance structure will be implemented:

1. An unstructured (UN) covariance matrix will be attempted first.
2. A heterogeneous Toeplitz covariance matrix will be attempted if the UN covariance matrix fails to converge.
3. A heterogeneous compound symmetry (CS) covariance matrix will be attempted if the heterogeneous Toeplitz covariance matrix fails to converge.
4. A homogeneous CS covariance matrix will be attempted if the heterogeneous CS covariance matrix fails to converge.

If the UN covariance matrix converges, the Kenward-Roger approximation will be used to estimate the denominator degree of freedom. Otherwise, under a more parsimonious structure, a modified covariance estimator will be used ([Gosho, Noma, and Maruo, 2021](#)).

The estimated change from baseline in hours of ventilation support at Week 24 will be summarized by AT132 dose level based on this model, including the standard error (SE) and 95% confidence interval (CI).

Participants who discontinue from the study prior to Week 24 due to death or due to lack of efficacy and who have missing observations after the intercurrent event occurs, will have those missing observations imputed by unfavorable values (i.e. 24 hours) in the analysis.

The primary analysis will be conducted using the FAS.

The hours of ventilation support and change from baseline will also be summarized descriptively by visit and AT132 dose level group.

A subject line plot of the hours of ventilation support at each time-point will be created.

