3.5 Removal of Subjects

3.5.1 Withdrawal of Subjects

It is critical to the integrity of this study that subjects adhere to the visit schedule outlined in this protocol and to complete all scheduled procedures. As such, the Investigator and clinic staff should make every reasonable effort to convey the importance of remaining on the study to the subject or parent(s)/LAR(s). Any subject withdrawing from the study should be reported as soon as possible to the Sponsor's Medical Monitor.

Subjects may withdraw from further participation in the study at any time and for any reason. Efforts will be made to collect important data, if feasible, and if the subject agrees.

Early withdrawal may occur for any of the following reasons:

- Subject request or withdrawal of consent
- AE
- Protocol deviation (at the Sponsor's discretion)
- Investigator discretion
- Study termination by the Sponsor
- Lost to follow up

In all cases, the reason(s) for study withdrawal will be recorded in the source document and on the appropriate electronic case report form (eCRF).

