7.4.2.1.2 Secondary Analysis

Based on the MMRM described in [Section 7.4.2.1.1](#), the change from baseline in hours of ventilation support at Week 1, 4, 12, 16, 36, and 48 will be summarized by treatment group.

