4.0	15-Apr-2024	Appendix 2 Unfavorable Values for Efficacy Estimand Imputation (5.2)	For the 3 rd column header "Imputed value after ICE occurrence through Week 24", "Week 24" has been updated to "Week 48".	For clarification purpose.

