1.1.3 Estimand

The estimand of the primary objective is defined by the following 5 attributes:

- Treatment: Single dose of AT132
- Population: Male participants with ventilator-dependent XLMTM, as defined by the inclusion/exclusion criteria of the study
- Endpoint: Change from baseline in hours per day of ventilation support at Week 24
- Intercurrent events and their corresponding strategies: For study discontinuation due to death or due to lack of efficacy, a composite strategy will be adopted, where participants with the intercurrent event before Week 24 having missing observation(s) after the intercurrent event will have those missing observations(s) imputed by unfavorable values ([Appendix 2](#))
- Population level summary: Mean change from baseline, by AT132 dose level

The estimand framework described above will be applied to all relevant primary and secondary efficacy endpoints.

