4.4.2.2.8 Survival

This endpoint will be summarized for low dose and the high dose groups separately for all participants in the FAS. Kaplan-Meier plots of time from the dosing date to event will be provided. In addition, the estimated survival rate at the following time-points will be presented by dose level group:

- 3 months
- 6 months
- 1 year
- 2 years
- 5 years
- 10 years

For this analysis, the date of a participant's death is considered the time of an event. Survival status should be assessed at each visit until the participant withdraws consent or completes the study. If the participant misses a visit or withdraws for a reason other than withdrawal of consent or death, the site should contact the parent(s)/LAR(s) to ascertain if the participant is

alive. For participants who withdraw from the study, the participant should be contacted every 6 months for 5 years after administration and every year for an additional 5 years (after the 5-year follow-up through 10-years follow-up) to assess for survival. If not alive, the cause and date of death should be requested and recorded.

Participants will be censored at the last known date/time of contact.

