5.2 Appendix 2 Unfavorable Values for Efficacy Estimand Imputation

Endpoint	Variable	Imputed value after ICE occurrence through Week 48
Primary	Hours of ventilation support	24 hours
Key Secondary	Achieving functionally independent sitting for at least 30 seconds	No (0)
Secondary	CHOP INTEND Total Score	0
	MIP	0
	Myotubularin expression	0
	ACEND total score	0
	PedsQL Scale	0
	PedsQL Summary Score	0
	Number of age-appropriate gross motor function milestones achieved	0
	Full ventilator independence achieved	No

ICE = intercurrent event

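### The 24-hour imputation depends on a withdrawal reason recorded before Week 24, while Appendix 2 runs the imputed values to Week 48, so known deaths are handled by different rules

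*SAP*

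**What the plan says.** - SAP 1.1.3 adopts a composite strategy for study discontinuation due to death or lack of efficacy, limited to "participants with the intercurrent event before Week 24 having missing observation(s) after the intercurrent event". Protocol 2.1 has the same limit. SAP 1.1.3 extends the framework to the relevant secondary efficacy endpoints.
- SAP 4.3.2 applies it to the primary endpoint: "Participants who discontinue from the study prior to Week 24 due to death or due to lack of efficacy", if later data are missing, "will have those missing observations imputed by unfavorable values (i.e. 24 hours) in the analysis". The model includes Weeks 24, 36 and 48. The model estimate is reported at Week 24, and hours are also summarised descriptively by visit.
- The column of values in SAP Appendix 2 is headed "Imputed value after ICE occurrence through Week 48". The version history shows that the horizon in this header was moved from Week 24 to Week 48 in SAP 4.0, as a clarification. The event cut-off in 1.1.3 and 4.3.2 is before Week 24.
- Protocol 7.4.2.1.2 adds, from the same model, that "the change from baseline in hours of ventilation support at Week 1, 4, 12, 16, 36, and 48 will be summarized by treatment group".
- Protocol 3.5.1 states "Early withdrawal may occur for any of the following reasons" and gives six: subject request or consent withdrawal, AE, protocol deviation, investigator discretion, sponsor termination and loss to follow-up. Neither death nor lack of efficacy is among them.
- SAP 4.4.2.2.8: "For participants who withdraw from the study, the participant should be contacted", six-monthly for five years after dosing and then yearly, with cause and date of death requested. Protocol 5.1.1.25 says the same.

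**The concern.** A composite strategy treats death as a bad outcome in its own right, so it should apply to every death in the period it covers. Here two other things decide whether a death counts: the reason recorded when the child left the study, and whether the event fell before Week 24 even though the imputed values run to Week 48.

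The groups are small, four deaths are reported, and the Week 24 mean by dose, with its standard error and confidence interval, is the main efficacy result. The way one child is classified can move it visibly. The sensitivity analysis in SAP 4.3.3 keeps the same imputations, so it cannot expose the problem.

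**Working it through.** **1. The rule applied to three courses**

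| Course | Week 24 | Weeks 36 and 48 |
|---|---|---|
| Dies at Week 23, discontinuation due to death | 24 h | 24 h |
| Dies at Week 25 | observed value kept | missing |
| Withdraws after Week 16 for another reason, dies before Week 24 | missing | missing |

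No other rule fills the missing cells, so the MMRM treats them as missing at random.

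**2. Inputs**

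- High-dose n = 17 (Protocol 1.4.2, cutoff 08 July 2020).
- Low-dose n = 7, inferred: 6 children at that cutoff (Protocol 1.4.2), plus 3 controls then undosed (SAP 1.2), minus 2 never dosed (SAP 1.3). This assumes no replacement child was enrolled.
- Baseline 20.5 h, SE 2.02, n = 6, low dose (Protocol 1.4.2). It is used for both groups.
- Mean change -13 h and SD 6.0, borrowed from the retained sample size text (SAP 4.9). That text's N = 10 reproduces: two-sided t-test power is 0.724 at 4 per arm and 0.850 at 5 per arm.
- Deaths: 3 high dose, 1 low dose (Protocol 1.5). Timing relative to Week 24 is not given.

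**3. Arithmetic for the Week 24 mean**

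An imputed child has a change of 24 - 20.5 = +3.5 h; the others average -13 h. Imputing one child rather than leaving him out shifts the mean by (3.5 + 13)/n = 16.5/n:

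- n = 17: 16.5/17 = 0.97 h
- n = 7: 16.5/7 = 2.36 h

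**4. Illustrative MMRM**

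The model had an unstructured covariance and was fitted by maximum likelihood to 60 simulated data sets with 7 low-dose and 17 high-dose children. Assumed, not taken from the documents: mean changes of 0, -2, -6, -9, -13, -15 and -16 h at Weeks 1, 4, 12, 16, 24, 36 and 48, and a correlation of 0.9 between adjacent visits. Hours were bounded at 0 and 24. One high-dose child on the mean trajectory was recoded under each rule. High-dose model means:

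| Course | Rule | Week 24 | Week 36 | Week 48 |
|---|---|---|---|---|
| Death at Week 23 | as written (imputed) | -11.68 | -13.13 | -13.68 |
| Death at Week 25 | as written (missing) | -12.65 | -14.19 | -14.77 |
| Death at Week 25 | if imputed | -12.67 | -13.14 | -13.69 |
| Other withdrawal, then death | as written (missing) | -12.64 | -14.18 | -14.76 |
| Other withdrawal, then death | if imputed | -11.68 | -13.13 | -13.68 |

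- Other withdrawal, then death: Week 24 differs by 12.64 - 11.68 = 0.96 h, in line with step 3.
- Death at Week 25: Week 24 differs by 0.02 h, Week 36 by 14.19 - 13.14 = 1.05 h, and Week 48 by 14.77 - 13.69 = 1.08 h.

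**5. The other reading of Appendix 2**

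The header could also mean an event that occurs at any time up to Week 48. A Week 25 death would then be imputed, but the header would contradict 1.1.3 and 4.3.2. The text needs reconciling on either reading.

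**The case against.** The Week 24 cut-off fits the estimand: the endpoint is the change at Week 24, and a death after that visit cannot undo an observed value. A reader might infer that children outside the rule vanish from the analysis, or that late deaths distort the primary result. The documents support neither. These children stay in the FAS, contribute their earlier visits to the MMRM, and are counted under Survival and in the safety tables. A Week 25 death moves the Week 24 estimate by about 0.02 h.

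It is also tempting to say that the reported Week 36 and 48 means definitely mix two rules. The SAP presents the model result at Week 24 only and, under Protocol 7, prevails over Protocol 7.4.2.1.2. It does not say whether the descriptive by-visit tables use imputed values.

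Nor does the list in Protocol 3.5.1 show that no death can trigger the rule. Protocol 5.1.1.25 and SAP 4.4.2.2.8 both speak of death as a reason for withdrawal. With a single infusion, an AE does not by itself require leaving follow-up, and no child is reported who withdrew alive and then died before Week 24. There is no hypothesis test.

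All of this stands and narrows the point. What survives is that the trigger is the reason for discontinuation, so a known death after withdrawal for another reason falls outside a strategy meant to cover death, and that the event cut-off and imputation horizon differ.

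**Conclusion.** The concern holds in two limited parts.

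(a) Primary Week 24 estimate. A child withdrawn for another recorded reason and known to have died before Week 24 is left missing at random. The mean is then too favourable by about 1.0 h per such child of 17, or about 2.4 h per child of 7. This rests on the 20.5 h baseline, the -13 h change in the others and, for the low dose, the inferred n. The actual effect may be zero.

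(b) Weeks 36 and 48. Deaths before Week 24 are imputed and deaths between Weeks 24 and 48 are not. Any summary at those visits that uses imputed values mixes two rules, by about 1 h per child of 17 under the assumed trajectory. For endpoints other than hours, this applies only where a visit exists: MIP has no Week 36 assessment.

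A reader might size (b) by placing all three high-dose deaths after Week 24. With survivors assumed at 8 h, the mean would be (14 x 8 + 3 x 24)/17 = 10.8 h rather than 8.0 h, a gap of 2.8 h. The documents do not give the timing of the deaths. That figure is a worst case, and zero is equally compatible with the text.

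**What to change.** In SAP 1.1.3, 4.3.2 and Appendix 2:

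- Define the event as death from any cause, whatever withdrawal reason was recorded and whenever the death is learned of, or discontinuation for lack of efficacy. Take dates of death from the survival follow-up.
- Use one matching event cut-off and imputation horizon: through Week 48 if Weeks 36 and 48 are to be imputed.
- Apply the Appendix 2 values at each endpoint's own scheduled visits after the event.
- State whether the by-visit tables use imputed values.

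Protocol 2.1 carries the same Week 24 limit, so record the departure in the CSR. Say there that the change was made in an open-label study with the deaths already known.

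The cost is SAP wording and programming; no new data are needed. Where the rule bites, the means become less favourable.
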